1.2 SCHEMA

Figure 1. Study Schema for Protocol ANB020-006

Legend:

Etokimab = blue line

Primary endpoints assessed = red type

Placebo = yellow line

Gray shading = nontreatment period

NOTE: MFNS will be provided to all subjects as standard of care for all 3 groups.

Abbreviations: MFNS=Mometasone Furoate nasal spray

SC=subcutaneous(ly)

1.3 SCHEDULE OF ACTIVITIES (SOA)

Phase	Screening	Treatment				Safety Follow-Up			
Week	-4 to 0	0	1 ^a	4	8	12	16/EOT	20	24/EOS/ETV
Study Day	-31 to -20*	1d	5± 1d	29±3d	57±3d	85±3d	113±5d	141±5d	169±5d
Visit	1	2	3	4	5	6	7	8	9
Informed Consent	Х								
IXRS: Subject Screening/Randomization/Drug Dispensing/Treatment Completion	Х	Х		Х	Х	Х	Х		
Inclusion/Exclusion Criteria ^b	Х	Х							
Medical History (Including Prior CRSwNP Therapy)	Х								
Height	Х								
Physical Examination ^c	Х	Х					Х		Х
Vital Signs Including Weight ^d	Х	Х		Х	Х	Х	Х	Х	Х
12-Lead ECG ^e	Х	Х					Х		Х
Follicle Stimulating Hormone ^f	Х								
Pregnancy Test ^g	Х	Х		Х	Х	Х	Х	Х	Х
Drugs of Abuse (urine), HIV, Hepatitis B and C Viral Testing, TB Test (QuantiFERON® Gold) ^h	Х								
Hematology, Chemistry ⁱ	Х	Х	Х	Х	Х	Х	Х		Х
Urinalysis	Х	Х					Х		Х
Study Drug Injection ^j		х		Х	Х	Х			
Pharmacokinetics ^k		Х	Х	Х	Х	Х	Х	Х	Х
Immunogenicity ^I		Х		Х	Х	Х	Х	Х	Х
FEV ₁ (Spirometry) ^m		Х		Х	Х	Х	Х		
ePRO Device Dispensation/Collection ⁿ		Х							Х

Phase	Screening	Treatment Safety Follow-Up							
Week	-4 to 0	0	1 ^a	4	8	12	16/EOT	20	24/EOS/ETV
Study Day	-31 to -20*	1d	5± 1d	29±3d	57±3d	85±3d	113±5d	141±5d	169±5d
Visit	1	2	3	4	5	6	7	8	9
NPIF readings collected via Diary ^o	←								
Adverse Event Monitoring		←							
Concomitant Therapy ^p	←								
Nasal Endoscopy (centralized Nasal Polyp Score)b, w	Х	х		Х	Х	Х	Х		Х
CT Scan (Lund & 3D- correct accordingly) ^x		Х					Х		
Smell Test (UPSIT) ^q		Х			Х		Х		
SNOT-22	Х	Х		Х	Х	Х	Х		Х
Visual Analogue Scale (VAS)					X (Wee	ekly via ePi	ro Device)		
QoL (SF-36, EQ-5D)		Х		Х	Х	Х	Х		Х
Nasal Polyps Related Resource Questionnaire		Х		Х	Х	Х	Х		х
ACQ-7 ^r		Х		Х	Х	Х	Х		Х
Nasal Polyp Biopsies s, t		Х					Х		
Stored DNA Sampling t, u		х							
Whole Blood RNA Sampling ^{t,u}		Х		Х			Х		Х
MFNS – distribute and verify usage ^v	←	←							

Abbreviations: ACQ-7 = 7-item Asthma Control Questionnaire; CRSwNP = Chronic Rhinosinusitis with Nasal Polyposis; d = day(s); CT = computed tomography; DNA = deoxyribonucleic acid; ECG = electrocardiogram; EOS = End of Study; ePRO = electronic patient-reported outcome; EQ-5D = EuroQol-5D for measuring QoL; ETV = Early Termination Visit; HIV = human immunodeficiency virus; IXRS = Interactive Web Response System; NPIF = nasal peak inspiratory flow; QoL = quality of life; SF-36 = Short Form-36 Health Assessment; SNOT-22 = Sino-Nasal Outcome Test; TB = tuberculosis; UPSIT = smell identification test; VAS = visual analogue scale.

Footnotes on the next 2 pages.

- * During the screening window patients must use MFNS for a minimum of 20 days prior to Day 1 (maximum screening window is 31 days). Screening procedures can be conducted up to Day -1 if necessary.
- ^a Visit must occur 5 days (±1 day) after Visit 2.
- b Inclusion/exclusion criteria are based on all screening assessments, Visit 1 nasal endoscopy, and laboratory results. Week 0/Day 1 pre-dose assessments are to be reviewed before enrollment.
- ^c A complete physical examination will be performed at the screening visit. All other physical examinations should be abbreviated and address associated complaints or findings and any other assessments required to evaluate adverse events.
- d Vital signs assessments should be performed before blood sampling and before injection of study drug at each study visit where administered. Blood pressure readings should be obtained after approximately 15 minutes of rest in a seated position.
- e 12-Lead ECG should be performed after 10 minutes of rest in a supine position and before the blood sample is collected. ECG must be conducted on ECG machine provided by ERT for the ANB020-006 clinical trial.
- ^f Follicle stimulating hormone may be used to confirm menopausal status in female subjects as needed.
- Pregnancy testing is only required for women of childbearing potential (WOCBP). A serum test will be performed at the screening visit; urine pregnancy tests will be performed at treatment and follow-up visits. Testing must be performed before injection of study drug at Weeks 0, 4, 8, and 12. A negative result must be obtained at Visits 1 and 2 before subject may be randomized.
- h HIV 1 and 2, hepatitis B surface antigen, hepatitis B core antibody, hepatitis C antibody, and *Mycobacterium tuberculosis* (TB) will be assessed. Subjects with an indeterminate QuantiFERON® TB Gold result at Screening will be allowed 1 retest.
- ¹ Hematology and chemistry: Blood samples will be taken before injection of study drug, after the ECG and vital signs assessments.
- Subject is required to remain onsite for 2 hours post-dose for observation at Week 0 (Day 1). Subjects with any ongoing treatment-emergent AEs or SAEs at the time of scheduled discharge from the study center should remain at the study center until the Investigator has determined that these events have been resolved or deemed as not clinically significant. Subjects are not required to remain onsite after follow-up injections (Weeks 4, 8, and 12) unless deemed necessary by the Investigator, if there have been injection site reactions, or other AEs are noted.

8

- ^k Pharmacokinetics blood samples will be collected for all subjects at the following time points:
 - Visit 2/Week 0: prior to dosing on Day 1.
 - Visit 3/Week 1: Visit 3 can occur 3 to 5 days after Visit 2.
 - Week 4, 8, 12: prior to dosing.
 - Week 16, 20, and 24: any time at each visit.
- Immunogenicity blood samples will be collected for all subjects at the following time points:
 - Visits 2 (Week 0), 4 (Week 4), 5 (Week 8), and 6 (Week 12): prior to dosing.
 - Visits 7 (Week 16), 8 (Week 20), and 9 (Week 24): any time at each visit.

- All subjects should have the result of FEV₁ (% of predicted normal as defined by the Global Initiative for Asthma) recorded in the source on Day 1 and at all the other scheduled visits during the treatment period. Every effort should be made to perform FEV₁ assessment at the same time at each visit. If a subject with active asthma's FEV₁ \leq 60% on Day 1, then the subject will not be randomized. FEV₁ assessment should be conducted on the spirometry machine provided by ERT for the ANB020-006 clinical trial.
- The ePRO device will be provided to subjects on Day 1 upon confirmation of randomization. Subjects should be trained on log in and completion of NPIF distribution within the ePro device. The subjects should bring the ePRO device to each visit. The ePRO device should be returned to the site at the Week 24 (EOS) visit. Detailed instructions will be provided separately in the Procedures Manual.
- Peak Nasal Inspiratory Flow Meters will be provided to patients during the screening visit and patients will be instructed on use and recording requirements. NPIF values will be recorded on a paper diary during Screening (for 1 week/7 consecutive days). Diary must be returned to the study coordinator at the Day 1 dosing visit. Following randomization, eDiaries will be distributed and NPIF values will be recorded directly in the device.
- ^p Concomitant therapy will include pharmacologic and nonpharmacologic therapies.
- ^q Testing must be performed before injection of study drug at Weeks 0 and 8.
- The ACQ-7 will be assessed only in subjects with an active asthma disease.
- 5 Optional polyp biopsies will be collected from subjects who indicate approval on ICF, in study centers with the capability to conduct the procedure.
- t Samples will be collected before injection of study drug on Day 1.
- Optional sampling for exploratory analysis of DNA and RNA, requiring separate pharmacogenetic consent acknowledgment in ICF.
- MFNS bottles will be distributed and used bottles collected at monthly visits to assess use. Subjects should be approximately 80% compliant with usage during Screening and throughout the study. During Screening subjects must complete a minimum of a 20 day run-in using MFNS prior to Day 1.
- * Endoscopy can utilize study windows to ensure procedure can be completed prior to dosing. Day 1 Endoscopy can occur up to 5 days prior to Day 1 clinic visit. If endoscopy is performed on site it should be completed after all other study assessments are done and prior to dosing on dose days.
- X Day 1 CT must be collected prior to dosing on Day 1. If necessary, the Day 1 CT can be collected during Screening, prior to Day 1, however all efforts should be made to conduct CT after subject screening labs have been reviewed and it is determined subject is likely eligible for the study. Note: CTs collected within 3 months prior to randomization (Day 1) can be utilized in lieu of a new Day 1 CT if the necessary imaging requirements are present.

9

y Day 1 spirometry should be assessed prior to randomization to ensure inclusion/exclusion criteria are met

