- 22. Planned surgery during the study or within 30 days before Screening.
- 23. History of malignancy within 5 years, except non-melanoma skin cancer that has been fully treated with no current active disease.
- 24. Initiation of allergen immunotherapy:
 - a) Within 12 weeks prior to Screening
 - b) Planned to begin therapy during the screening period
 - c) Planned to begin during the randomized treatment period

Subjects who started immunotherapy more than 12 weeks prior to Screening can continue the immunotherapy during the study providing dosing is at least 2 weeks prior to each dose of study drug.

- 25. Undergone any nasal surgery (eg, any procedure with excision of tissue) within 3 months before randomization (Day 1).
- 26. Evidence of drug/substance abuse that would pose a risk to subject safety, interfere with the conduct of the study, or affect the subject's ability to participate in or comply with the study protocol, including but not limited to evidence of misuse of addictive drugs, such as opioids, outside of prescribed medications for a medical condition.

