8.1.1 NASAL ENDOSCOPY AND NASAL POLYP SCORE

Nasal endoscopy is one of the co-primary endpoints in the study (ie, change in NPS from baseline to Week 16). It will be performed according to the SoA (see Section 1.3), if the endoscopy is performed onsite during the study visit, it should occur after study assessments (eg, QoL assessments, labs, UPSIT, etc.) have been completed and preceded by local administration of anesthetic drugs in combination with a decongestant. The nasal endoscopy must be performed prior to dosing on Day 1, Week 4, Week 8, and Week 12. The Day 1 endoscopy can be scheduled up to 5 days prior to the Day 1 visit; visit windows can be utilized for scheduling follow-up nasal endoscopies. For the analysis of primary endpoint, central reading of Day 1 will be used for comparison with central reading at Week 16. The sites will remove subject-identifying information from the imaging data header and label with subject ID prior to sending the imaging data to the central reader.

Standard video sequences of the nasal endoscopy will be downloaded or sent to a Sponsor-designated centralized reader at the completion of the visit for adjudication. Nasal endoscopy will be performed using centralized imaging data assessments and scoring by an independent reviewer for the imaging data will be performed for all endoscopies. To confirm eligibility at Study Day 1, only the screening visit pass/fail results will be made available to the study center. The final results of central reading will be made available after the study.

Further details on nasal endoscopy will be available in a separate operational manual provided to the sites.

A sample NPS is provided in Appendix D.

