8.1.6 POLYP BIOPSIES

Study centers with the capability to perform a nasal polyp biopsy and with consent of the subject, will collect samples as noted below.

A baseline biopsy will be obtained at Day 1 (Week 0) of the study (before injection of the study drug). After randomization, another biopsy of nasal polyp tissue will be obtained at Week 16.

The complete details on tissue collection and processing will be provided separately. Briefly, the biopsied polyp tissue will be weighed (mg) and then cut into cubes of approximately 0.5 cm in each dimension. All but one cube will be individually placed into labeled cryotubes and immediately frozen with liquid nitrogen, and then maintained at -70°C or colder until shipped on dry ice to a central storage site or laboratory. Nasal polyp tissue will be subsequently assessed for various biomarkers of inflammation and disease process or response. Any remaining tissue will be discarded within 5 years of the completion of the last visit for the last patient in the study. Additional information on collection, processing, storage, and shipment of samples is located in the laboratory manual.

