8.4 BIOMARKERS

No specific or exploratory biomarkers will be collected or analyzed in this study.

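### Read literally, the visit-order rule can put the on-site Week 16 endoscopy after the optional polyp biopsy, and neither document says how a polyp score taken after tissue removal is handled

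*Protocol*

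**What the plan says.** **Order of the endoscopy.** Protocol 1.3, footnote w: "If endoscopy is performed on site it should be completed after all other study assessments are done and prior to dosing on dose days". SAP Table 1 carries the same sentence. Protocol 8.1.1 gives the rule with examples: "it should occur after study assessments (eg, QoL assessments, labs, UPSIT, etc.) have been completed". The rule covers endoscopies done on site. For the others, 8.1.1 allows flexibility: "The Day 1 endoscopy can be scheduled up to 5 days prior to the Day 1 visit", and "visit windows can be utilized for scheduling follow-up nasal endoscopies". The Week 16 window is Day 113 plus or minus 5 days.

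**Biopsy.** It has its own row in the Schedule of Activities at Day 1 and Week 16, and its section (8.1.6) sits under Efficacy Assessments. It is optional and limited to consenting subjects at centers able to do it. The Day 1 biopsy is ordered only relative to the injection. For the second, 8.1.6 says: "After randomization, another biopsy of nasal polyp tissue will be obtained at Week 16". The tissue is "cut into cubes of approximately 0.5 cm in each dimension"; no total amount is stated.

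**Scoring and re-takes.** Appendix D grades each nostril 0 to 4 on polyp size and reach, and the two scores are summed. SAP 8.1.1 says that an unreadable Week 8 or Week 16 image should be repeated and that the repeat is analysed. It makes no exception for a repeat after a biopsy, and the SAP has no other rule for post-biopsy scores.

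**The concern.** NPS measures the tissue that a biopsy removes. If tissue comes out before the video, the score can fall for a reason unrelated to treatment.

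There are two routes:

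- **Week 16.** Footnote w, applied as written, puts the on-site video last, after the biopsy. A re-taken video can have the same result at a site that scoped first.
- **Day 1.** If the baseline endoscopy is done before the Day 1 visit, it precedes the biopsy. Weeks 4, 8, 12 and 16 are then all compared with a baseline that still includes the excised tissue, whatever the order at Week 16.

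The co-primary NPS change and the NPS responder endpoint are exposed to both routes. Time to first NPS response, first in the secondary hierarchy, is exposed mainly to the Day 1 route. Because biopsy depends on site and consent, any effect would sit in a subset and vary between sites.

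**Working it through.** **1. The visit sequences that the text permits for a biopsied subject**

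| Day 1 endoscopy | Baseline NPS is | Week 16 on-site endoscopy, footnote w read literally |
|---|---|---|
| On site on Day 1, rule read literally | after the Day 1 biopsy | after the second biopsy |
| Up to 5 days early | before the Day 1 biopsy | after both biopsies |

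In the first row the two visits follow the same order. The effects cancel only if the Day 1 tissue has regrown by Week 16, and the documents do not address regrowth. In the second row they cannot cancel by design. A site that scopes before the Week 16 biopsy removes the second excision from the score but not the first.

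**2. Scale for one subject.** A one-grade fall in one nostril is 1 NPS point. That is 1/1.3 = 77% of the design difference (Protocol 9.2) and equals the responder cut-off of 1 point. This is a per-subject figure, not an effect on the trial estimate.

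**3. The plan's own power.** Inputs from Protocol 9.2: difference 1.3, SD 1.5, n = 27 per arm, 2-sided 5%. Noncentrality = 1.3 / (1.5 × √(2/27)) = 3.18 on 52 degrees of freedom. Power is 0.878 by noncentral t and 0.890 by the normal approximation. The stated figure of about 87% is reproduced.

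**4. Equal uptake and equal shift across arms.** Neither figure is in the documents; both are assumed. With a fraction f biopsied and a shift of d points, each arm mean moves by f × d. This cancels from the difference, and only the spread grows: SD = √(1.5² + f(1−f)d²).

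| f | d | SD | Power |
|---|---|---|---|
| 10% | 0.5 | 1.507 | 0.875 |
| 10% | 1 | 1.530 | 0.865 |
| 25% | 0.5 | 1.516 | 0.871 |
| 25% | 1 | 1.561 | 0.851 |
| 50% | 0.5 | 1.521 | 0.869 |
| 50% | 1 | 1.581 | 0.842 |

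A 2-point shift, a stress case, gives 0.827 at 10% uptake and 0.739 at 50%.

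**5. Unequal uptake at Week 16.** Here the difference itself moves, by (excess rate) × d. The SD is held at 1.5 and the excess is assumed to be in the placebo arm.

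- 10-point excess, shift 0.5: 1.3 − 0.05 = 1.25, power 0.852.
- 10-point excess, shift 1: 1.3 − 0.10 = 1.20, power 0.822.
- 20-point excess, shift 1: 1.3 − 0.20 = 1.10, power 0.753.

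An excess in an active arm would move the difference the other way and inflate it.

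**The case against.** The strongest reply is that no passage says the biopsy is among the assessments that must come first. The examples in 8.1.1 are questionnaires, laboratory samples and the smell test. The same sentence has local anaesthetic and a decongestant given before the scope, so the likely purpose is to keep those from disturbing symptom, smell and laboratory results. Sections 8.1.6 and 8.1.1 also defer detail to separate documents, either of which might set the order. The rule is worded as a recommendation and covers only on-site endoscopies, and biopsy is optional.

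Much of this stands. It limits the issue to a subset of unknown size and rules out saying that the Week 16 NPS of the trial is scored after excision. It does not remove the problem. The list of examples is open-ended, the biopsy is a scheduled efficacy assessment, and a site following footnote w as written would scope last. The Day 1 route and the re-take route do not depend on how footnote w is read.

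Three stronger readings are tempting and not supported:

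- **A bias toward no effect, because placebo subjects keep more polyp to biopsy.** Consent and site capability do not depend on arm, and treatment is blinded. A Week 16 biopsy does need residual polyp, so rates could differ if the drug works, but entry requires an NPS of at least 4 and the assumed effect is 1.3. Nothing in the documents gives a differential rate.
- **A large excision.** The cube size is stated but the number of cubes is not. A full-grade fall after biopsy is an assumption.
- **The biopsy as prohibited surgery.** Exclusion 25 concerns procedures before randomization, and Appendix A lists therapies barred on study. Neither classifies a research biopsy that the protocol itself schedules.

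**Conclusion.** The point holds as a gap in the measurement sequence. The written rule permits, and read literally directs, a co-primary score to be taken after tissue removal in the biopsied subset. The early baseline endoscopy creates a second, independent mismatch, and the SAP handles neither.

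Its size cannot be established. With biopsy rates and shifts equal across arms, the treatment difference is not biased and the power loss is small: 0.878 to 0.875-0.842 over 10-50% uptake and a 0.5-1 point shift. Bias requires Week 16 biopsy rates that differ by arm, and its direction would follow the sign of that difference. All of these figures rest on assumed uptake and assumed shift. A reader might infer that the co-primary result is compromised; the documents do not support that. They support correcting the order, because the correction is cheap and the endpoint is co-primary.

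**What to change.** 1. **Week 16.** In footnote w, Protocol 8.1.1, Protocol 8.1.6 and SAP Table 1, state that the Week 16 biopsy is taken only after that visit's video endoscopy is complete and, where possible, confirmed readable. The second condition limits post-biopsy re-takes.
2. **Day 1.** Reconcile footnote w, 8.1.1 and 8.1.6 so that biopsy and baseline endoscopy come in the same order for all biopsied subjects. The Week 16 order should not simply be copied to Day 1: scoping first would put the first excision after baseline for every biopsied subject and carry it into every later NPS. Scoping after the biopsy would not be compatible with the early-endoscopy allowance for those subjects.
3. **Data.** Record biopsy date and side, so that scores and re-takes obtained after a biopsy can be identified.
4. **SAP 8.1.1.3.** Add a sensitivity run of the NPS co-primary and NPS responder analyses excluding subjects with a Day 1 pre-dose biopsy. Do not define the exclusion by the Week 16 biopsy, which is a post-randomization event that treatment could influence.
5. **Separate minor point.** Protocol 8.4 says "No specific or exploratory biomarkers will be collected or analyzed in this study", while 8.1.6 plans biomarker work on the polyp tissue. Reconcile the two.

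The cost is a few sentences on visit order, two data fields and one additional run. That run has fewer subjects and so less precision.

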2 INTRODUCTION

2.1 STUDY RATIONALE

Chronic rhinosinusitis (CRS) is a heterogeneous disease which manifests with mucosal inflammation of the nasal cavity and paranasal sinuses. Chronic rhinosinusitis can be divided into 3 distinct clinical syndromes: CRS with nasal polyposis (CRSwNP) accounting for 20 to 33 percent of all CRS cases, and CRS without nasal polyposis and allergic fungal rhinosinusitis accounting for 60 to 65% and 8 to 12% of all CRS cases, respectively (*Meltzer et al., 2004*). CRSwNP is characterized by the presence of multiple polyps in the upper nasal cavity, originating from the ostiomeatal complex. It is the most aggressive form of CRS and causes significant morbidity and leads to a diminished quality of life in CRS patients.

Current treatment options for CRSwNP are limited and typically include nonsystemic treatment with nasal corticosteroids, systemic corticosteroids, antibiotic therapy, and the surgical removal of polyps. Many patients achieve disease control with these standard nonsystemic treatments. However, due to disease severity, treatment-related adverse reactions, or other factors, some patients do not achieve adequate disease control. Relapses after surgery are common in patients with CRSwNP, and thus, there is need for long term therapeutic control in CRS patients.

CRSwNP is often associated with other atopic diseases, with up to 50% of CRSwNP presenting with comorbid asthma (*Jarvis et al., 2012*) though the contributions of these acute conditions to the development of CRSwNP is not well understood. Asthma has been the most well-defined; approximately 88% of patients with asthma also have radiographic evidence of sino-nasal inflammation and approximately 26 to 48% of patients with asthma also have been diagnosed with CRSwNP. Increased asthma severity has been linked to enhanced sino-nasal inflammation (*Stevens, et al., 2016*).

The close association of CRSwNP with atopic disorders, particularly asthma, has led to a series of clinical studies with biologics that have shown efficacy in asthma. Two anti-IL-5 monoclonal antibodies (mepolizumab and reslizumab) and anti-immunoglobulin E (IgE) (omalizumab) have been tested in clinical studies in CRS patients with overall encouraging results (*Chiarella et al., 2017*). More recently dupilumab has also shown to provide benefit to CRSwNP patients (*Pauwels et al., 2015*). These studies have demonstrated the utility of biologics in CRSwNP as a viable option to provide much-needed new therapeutic approaches.

The underlying pathophysiology of CRSwNP is not well-defined. Several factors are thought to contribute to both the development of the disease and complications of treatment. An impaired sinonasal epithelial barrier could allow for increased exposure to inhaled pathogens and antigens, which, in the setting of a dysregulated host-immune response, could encourage chronic inflammation (*Stevens*, et al., 2016).

Interleukin-33 (IL-33), a tissue-derived cytokine that induces and amplifies eosinophilic inflammation, has emerged as a promising new drug target for asthma and allergic disease (*Smith et al., 2017*). Most recently, IL-33 has been detected in nasal polyps and a series of translational studies have highlighted

the potential central role of IL-33 in the pathogenesis of CRSwNP (*Song et al., 2017*; *Poposki et al., 2017*; *Zhang et al., 2017*). A recent study by Smith et al. resequenced 100 genes that were implicated in asthma to identify a novel sequence variant that directly correlated to eosinophil counts, as well as established asthma loci (IL-33 and IL1RL1) and demonstrated that asthma risk is mediated through IL-33 and eosinophil counts are subsequently reduced, which could reduce the recurrence of nasal polyps following surgery. This study provided a sound rationale for the inhibition of the IL-33 pathway as an effective avenue to contain asthma. Since patients with concurrent CRSwNP and asthma require more sinus surgeries than patients with CRSwNP alone (*Stevens, et al., 2016*), a significant clinical need to isolate and inhibit the IL-3 pathway is warranted.

Etokimab is a powerful and efficient inhibitor of IL-33, and thus, etokimab potentially offers an additional and novel treatment approach to treat severe CRSwNP patients who fail to respond to the current therapies.

This Phase 2 study is intended to explore the activity of etokimab in adult subjects with CRSwNP. Etokimab is a highly effective inhibitor of IL-33, a cytokine that is considered to drive the pathogenic cascade in asthma, atopic dermatitis (AD), and CRSwNP. Interleukin-33 directly affects eosinophil counts and function by acting on the early phases of the atopic immune response, which is upstream of current asthma treatments with clinically validated targets such as IL-5, IL-4, and IL-13. The possibility to influence complementary and synergistic pathways involved in CRSwNP pathogenesis may provide a therapeutic improvement compared to the inhibition of single downstream pathways. This study will explore the effects of repeat doses of etokimab, administered subcutaneously (SC), compared to placebo on validated endpoints, such as the Nasal Polyp Score (NPS) and Sino-Nasal Outcome Test (SNOT-22).

